5.5.3 Antiemetics

Antiemetics will be used according to standard practices. Any 5-hydroxytryptamine (5-HT₃) receptor inhibitor (ex. ondansetron) combined with prochlorperazine or similar can be used during treatment, as needed.

5.5.4 Antimicrobial Prophylaxis

Patients should receive prophylaxis directed against gram-negative gastrointestinal infections (GI), Candidiasis/mold, Pneumocystis pneumonia (PCP), and/or herpes simplex virus (HSV), according to individual institutional practices.

5.5.5 Intrathecal Prophylaxis

Intrathecal prophylaxis must be used according to institutional standard practice for all patients with the choice of agent at the discretion of the investigator. Maximum doses of up to 15 mg of methotrexate, up to 100 mg of cytarabine, or 40 mg of cytarabine and 12 mg of methotrexate in triple therapy should be employed.⁹⁵⁻⁹⁷ Hydrocortisone 50 mg intrathecally can optionally combined with methotrexate if desired to lessen the risk of arachnoiditis. To reduce the risk of CNS leukemia relapse, intrathecal prophylaxis should be administered during screening and on day 29-35 of at least the first two cycles at the conclusion of blinatumomab infusion as activity of blinatumomab has not been established in patients with CNS leukemia. This schedule of CNS prophylaxis administration has been adopted from prior blinatumomab trials to avoid confounding neurologic events related to intrathecal chemotherapy administration during blinatumomab administration.³¹

5.5.6 Colony Stimulating Factors

The routine use of colony stimulating factors is disallowed. The use of colony stimulating factors in the presence of severe neutropenic infection should be used in accordance with ASCO guidelines and discussed with the study chair before implementation.⁹⁸

5.5.7 Management of Tumor Lysis Syndrome

Tumor lysis occurs as part of initial cytoreductive therapy. The most extreme form, TLS, is characterized by hyperuricemia, hyperphosphatemia, increased lactate dehydrogenase (LDH), coagulopathy, and a potential cytokine release syndrome. Since the occurrence of TLS is magnified in the presence of large tumor burdens, we will require prephase treatment as specified in 3.2.1 and 5.5.2 for any patient who has > 50% bone marrow blasts, $\geq 15,000/\mu\text{L}$ peripheral blood blasts, or an elevated LDH suggestive of rapidly progressive disease as per the investigator's assessment.

- To prevent hyperuricemia, all patients without known allergy will receive allopurinol 300-600 mg PO qday continuing through the period of maximal tumor lysis or other anti-uricemia regimen per institutional practice. Rasburicase may be used per institutional policy for hyperuricemia. Screening for G6PD deficiency should be obtained in susceptible populations before beginning Rasburicase.
- To decrease the risk of hyperphosphatemia, an oral phosphate binder per institutional practice (ex. sevelamer 400-800 mg) may be administered orally every 4-6 hours beginning on with prephase or protocol treatment and continued as tolerated until maximum tumor lysis has occurred.
- Cytokine release syndrome (CRS) can occur shortly after completion of blinatumomab infusion, accompany severe TLS, and present with fever, bronchospasm with dyspnea and/or respiratory distress, altered blood pressure, myalgias, arthralgias, tumor pain and/or urticarial rash. Any patient with cytokine release syndrome should receive 20 mg dexamethasone (or equivalent steroid) IV immediately. Tocilizumab may also be used at the discretion of the investigator for CRS as per section 5.5.2. and 5.5.8.1.

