	Grade 3	Infusion of the blinatumomab must be stopped immediately. Dexamethasone should be administered at a dose of at least 24 mg per day (8 mg every 8 hours orally or IV) for up to three days. The dexamethasone dose will then be reduced step-wise over up to four days. Hold blinatumomab until AE resolves to Grade ≤ 1 and for at least 3 days, then resume drug at 9 mcg/day. Escalate to 28 mcg/day after 7 days if the toxicity does not recur and if it resolved within 7 days. If the toxicity takes more than 7 days to resolve, do not escalate to 28 mcg/day. If toxicity occurs at 9 mcg/day or it takes more than 14 days

Toxicity - Adverse Event CTCAE v4.0 terminology	AE Grade	Action
		
to resolve, discontinue blinatumomab permanently. Infusion should be re-started in the hospital, under supervision of the investigator and the patient should remain hospitalized for at least two days. Within one hour prior to re-start of treatment and within one hour prior to any dose increases, patients must receive 20 mg of dexamethasone intravenously.
 
In the first three days after re-start, vital sign measurements and writing tests (Appendix G) should be performed.
 
If patient has already been dose reduced to 9 mcg/day dose for any reason and Grade 3 event occurs, blinatumomab should be discontinued permanently.

	Grade 4	
Infusion of blinatumomab must be stopped immediately.
 
Dexamethasone should be administered at a dose of at least 24 mg per day (8 mg every 8 hours orally or IV) for up to three days. The dexamethasone dose will then be reduced step-wise over up to four days. Blinatumomab should be discontinued permanently.

Seizure	Grade 1-3	
As per Grade 3 Nervous System/Psychiatric Disorders (above). Appropriate prophylactic / therapeutic doses of anticonvulsant treatment (e.g. phenytoin or levetiracetam) will be administered during subsequent infusions of blinatumomab. If seizure recurs discontinue blinatumomab permanently.

	Grade 4	Discontinue blinatumomab permanently
Cytokine release syndrome (CRS), Allergic reaction, Anaphylaxis, or Infusion related reaction	Grade 1	Continue therapy with supportive care, as per local institutional guidelines.

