	Grade 2	
The infusion of the blinatumomab must be stopped immediately.
 
Supportive care, as per institutional guidelines.
 
If the interruption is longer than four hours, re-start of the infusion should be performed in the hospital, under supervision of the investigator.
 
Within one hour prior to re-start of treatment and within one hour prior to any dose increases, patients must receive 20 mg of dexamethasone intravenously.

Toxicity - Adverse Event CTCAE v4.0 terminology	AE Grade	Action
	Grade 3	
The infusion of the blinatumomab must be stopped immediately.
 
Dexamethasone should be administered at a dose of at least 24 mg per day (8 mg every 8 hours orally or IV) for up to three days.
 
The dexamethasone dose will then be reduced step-wise over up to four days.
 
Hold blinatumomab until the toxicity resolves to Grade \leq 1, then resume drug at 9 mcg/day for one week. If toxicity remains Grade \leq 1, increase dose to 28 mcg/day to complete 28-day cycle of therapy. Within one hour prior to the re-start of treatment and within one hour prior to any dose increases, patients must receive 20 mg of dexamethasone intravenously.
 
If Grade 3 toxicity recurs after blinatumomab is resumed, stop drug permanently.
 
If the initial adverse event lasts >14 days without improvement, then blinatumomab will be permanently discontinued.

	Grade 4	Blinatumomab should be discontinued permanently.
Liver functions Aspartate aminotransferase increased, Alanine aminotransferase increased (AST, ALT); bilirubin increased	Grade 1-2	Continue at same dose level.
	Grade 3-4	
Hold blinatumomab until AE resolves to Grade \leq 1, then resume drug at 9 mcg/day for one week. If toxicity remains Grade \leq 1, increase dose to 28 mcg/day to complete the 28-day cycle of therapy. If Grade 3-4 toxicity recurs, stop the drug permanently.
 
Within one hour prior to the restart of treatment and within one hour prior to any dose increases, patients must receive 20 mg of dexamethasone intravenously.

Disseminated intravascular coagulation	Grade 2	Continue at same dose level.

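### Steroid treatment of cytokine release syndrome is instructed differently in Section 5.5.7, Section 5.5.8.1 and Table 6.2, and no text says which governs

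*Combined protocol and SAP*

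**What the plan says.** Three places in the protocol instruct sites on CRS after blinatumomab.

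- **Section 5.5.7 (tumor lysis syndrome).** A bullet describes CRS that may follow the end of the infusion or accompany severe tumor lysis, then says "Any patient with cytokine release syndrome should receive 20 mg dexamethasone (or equivalent steroid) IV immediately". It gives no grade and no duration. It adds that tocilizumab may be used, referring to 5.5.2 and 5.5.8.1.
- **Table 6.2 (Section 6.2.2).** One row is headed "Cytokine release syndrome (CRS), Allergic reaction, Anaphylaxis, or Infusion related reaction". Its action for a mild, grade 1 event is "Continue therapy with supportive care, as per local institutional guidelines". For a grade 2 event the infusion is halted at once, the care named is "Supportive care, as per institutional guidelines", and dexamethasone is tied to later steps: "Within one hour prior to re-start of treatment and within one hour prior to any dose increases, patients must receive 20 mg of dexamethasone intravenously". Grade 3: stop the infusion and give dexamethasone at a floor of 24 mg per day, oral or IV, for up to three days, then reduce stepwise. Grade 4: permanent discontinuation, with no steroid stated.
- **Section 5.5.8.1 (blinatumomab reactions).** Grade 1 is described as a mild reaction that needs no intervention, with treatment continued under local supportive care. Grade 2 stops the infusion and calls for institutional supportive care, and corticosteroids are among the listed examples of symptomatic treatment. Dexamethasone 20 mg IV is required before a dose increase, and before a re-start if the interruption was four hours or longer. Grades 3 and 4 both receive the dexamethasone course of at least 24 mg per day.

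**The concern.** CRS is an expected toxicity here: Section 5.3.1 says blinatumomab is known to cause it, and the premedication is there to reduce it. A site with a grade 1 case finds an instruction for an immediate IV steroid in one section and, in two others, supportive care only. A site with a grade 2 case finds the same instruction at onset in one section, and in the others a steroid that is optional at onset and required only later.

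Safety and tolerability are the primary objective (Section 1.1.1), and Section 13.3.1.1 tabulates adverse events by type and grade at each dose level. If treatment of the event depends on which section a site reads, cases summarised together may have been managed under different rules. Patients with the same event could also receive different care for no reason the protocol intends.

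**Working it through.** No sample size, power or event count is involved, so the check sets the texts side by side.

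| CRS grade | 5.5.7 | Table 6.2 | 5.5.8.1 |
|---|---|---|---|
| 1 | 20 mg dexamethasone (or equivalent) IV at onset | Continue; local supportive care; no steroid named | Same; intervention described as not needed |
| 2 | As above | Stop infusion; institutional supportive care; 20 mg before any re-start or dose increase | Stop infusion; institutional supportive care, corticosteroids a listed option; 20 mg before a dose increase, and before re-start only if interrupted four hours or longer |
| 3 | As above | Stop infusion; at least 24 mg/day for up to three days, then reduce | Same course |
| 4 | As above | Permanent discontinuation; no steroid stated | Permanent discontinuation; at least 24 mg/day for up to three days, then reduce |

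**Do the texts address the same event?** Table 6.2 names CRS. Section 5.5.8.1 is headed as hypersensitivity and infusion reactions and does not name CRS in its grade text, but 5.5.7 points to it for CRS, so the protocol itself treats it as applicable.

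**Grade 1.** An immediate IV steroid and no intervention are different instructions. This is the clearest conflict.

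**Grade 2.** The 20 mg dose in the graded sections is tied to re-start or dose increase, so it is premedication and not treatment at onset. Institutional care may include a steroid, but it need not. The difference is called for versus optional.

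**Grade 3.** The daily figure is consistent with its own schedule: 3 × 8 mg = 24 mg. It is a floor, so an immediate 20 mg dose followed by the course would satisfy both texts. Section 5.5.7 states no duration, so none is contradicted.

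**The graded sections against each other.** They differ in two ways:

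- At grade 4, 5.5.8.1 gives a dexamethasone course and the Table 6.2 row gives none.
- At grade 2, dexamethasone before re-start is unconditional in the Table 6.2 row but conditional on a four-hour interruption in 5.5.8.1. The opening text of 6.2.2 and Section 5.3.1 also carry the four-hour condition.

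**How many patients?** Section 7.1.1.1 lists CRS with blinatumomab in the band of at most 20%. The documents give no rate for the combinations. Assuming that band carried over, the ceiling would be 0.20 × 36 = 7.2, or about 7 of the maximum 36 patients in Section 13.5, with any number below that possible. At a dose level of 6 or 12 patients it would be 0.20 × 6 = 1.2 or 0.20 × 12 = 2.4. The combinations could raise the rate. How many cases would be treated differently between sites cannot be derived.

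**The case against.** The best defence is that a site would rarely be forced into a contradiction. Section 5.5.7 is advisory in tone and sits under tumor lysis. Supportive care under local guidelines neither forbids nor caps steroids. Section 5.5.8.1 says its recommendations may be modified locally, and 5.5.2 permits a brief steroid course for CRS. Sections 5.4 and 5.5.1 point to Section 6 for management and dose modification, and 6.1 sends questions to the Protocol Chair.

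Part of this stands. It is too much to say that a site cannot follow both texts at grade 2, and grade 3 is not a firm conflict. The rest does not remove the problem:

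- The 5.5.7 bullet also covers CRS after the end of the infusion, and then applies to every patient with CRS.
- Its reference to 5.5.8.1 concerns tocilizumab only.
- The references to Section 6 set no precedence for steroids in CRS, and the conservative-approach rule in 6.1 concerns dose reductions and delays.
- Permission to give a steroid is not the same as an instruction to give one at once.

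A reader might infer two larger consequences that the documents do not support.

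- **Distorted dose-limiting toxicity (DLT) counts.** A non-hematologic DLT under Section 5.4 needs grade 3 or higher and permanent discontinuation, and grade 3 or 4 events that force discontinuation in the blinatumomab run-in are excluded. The conflict is clearest at grades 1 and 2, which are not DLTs.
- **Material confounding of the T-cell studies.** Every patient already receives 20 mg dexamethasone at the start of each cycle and at the day 8 step, and some also have pre-phase dexamethasone. These endpoints are exploratory, and nothing in the documents sizes an added effect.

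**Conclusion.** The inconsistency is real and is in the current text. It is firm at grade 1 and present at grade 2. At grade 3 it is a difference of wording that can be read together. The two graded sections also disagree with each other on the grade 2 re-start dose and on a grade 4 steroid. No text says which section governs.

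It should be corrected because these are operative safety instructions for an expected toxicity and safety is the primary objective. Its size is a set of unreconciled instructions and not a patient count: the ceiling of about 7 of 36 rests entirely on the assumption that the blinatumomab band carries over to the combinations. A reader might infer that differing site practice would shift a sizeable share of a dose cohort. The documents contain no figure for that. This conclusion takes no view on which instruction is clinically right.

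**What to change.** Reconcile Sections 5.5.7 and 5.5.8.1 with Table 6.2 so that one grade-specific CRS instruction stands in one place and the others refer to it. It should cover:

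- whether the 5.5.7 sentence applies to all grades and settings;
- what is given at onset at grades 1 and 2;
- whether the grade 2 re-start dose depends on the length of the interruption;
- whether a steroid is stated at grade 4.

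The sponsor's clinical team decides the content.

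The cost is amendment wording and notice to sites. Sample size, endpoints and analyses are unchanged. No new steroid data collection is needed, because Section 5.5 already requires the case report form to capture all concurrent drugs.

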5.5.8 Hypersensitivity/Infusion Reactions

5.5.8.1 Blinatumomab

Reactions may manifest as fevers, chills, rigors, headache, rash, urticaria, angioedema, pruritis, arthralgias, hypo- or hypertension, bronchospasm, or other symptoms.

Treatment recommendations are provided below and may be modified based on local treatment standards and guidelines as medically appropriate:

Remain at bedside and monitor subject until recovery from symptoms.

• **For Grade 1 symptoms:** (Mild reaction; infusion interruption not indicated; intervention not indicated)

Continue therapy with supportive care, as per local institutional guidelines.

• **For Grade 2 symptoms:** Moderate reactions require therapy or infusion interruption but respond promptly to symptomatic treatment (e.g., antihistamines, non-steroidal anti-inflammatory drugs, narcotics, corticosteroids, bronchodilators, IV fluids). The infusion of blinatumomab must be stopped immediately.

Supportive care, as per institutional guidelines.

If the interruption is four hours or longer, re-start of the infusion should be performed in the hospital, under the supervision of the investigator. The subject should be observed overnight for possible side effects after the re-start, either in the hospital or in the outpatient setting as applicable.

Within one hour prior to start of treatment, or re-start of treatment if interruption is four hours or longer, and within one hour prior to any dose increases, patients must receive 20 mg of dexamethasone intravenously.

• **For Grade 3 symptoms:** (Severe reactions)

The infusion of blinatumomab must be stopped immediately.

Dexamethasone should be administered at a dose of at least 24 mg per day (8 mg every 8 hours orally or IV) up to three days. If symptoms persist, then tocilizumab may be used at the investigator's discretion as per 5.5.2.

The dexamethasone dose will then be reduced step-wise over up to four days.

Hold blinatumomab until toxicity resolves to grade ≤ 1 , then resume drug at 9 $\mu\text{g}/\text{day}$ for one week. If toxicity remains grade ≤ 1 , increase dose to 28 $\mu\text{g}/\text{day}$ to complete the 28-day cycle of therapy.

Within one hour prior to re-start of treatment and within one hour prior to any increases, patients must receive 20 mg of dexamethasone intravenously.

If grade 3 recurs after blinatumomab is resumed, stop drug permanently.

If the initial adverse event last for ≥ 2 weeks without improvement, then blinatumomab will be permanently discontinued.

• **For Grade 4 symptoms:** (Severe reactions)

The infusion of blinatumomab must be stopped immediately and permanently.

Dexamethasone should be administered at a dose of at least 24 mg per day (8 mg every 8 hours orally or IV) up to three days. If symptoms persist, then tocilizumab may be used at the investigator's discretion as per 5.5.2.

The dexamethasone dose will then be reduced step-wise over up to four days.

Investigators should follow their institutional guidelines for the treatment of anaphylaxis. Remain at bedside and monitor subject until recovery from symptoms.

5.5.8.2 Nivolumab and Ipilimumab

NOTE: The same infusion reaction guidelines apply to ipilimumab. Any reference to nivolumab below should be used also for considerations of ipilimumab-related infusion reactions.

Since nivolumab contains only human immunoglobulin protein sequences, it is unlikely to be immunogenic and induce infusion or hypersensitivity reactions.

However, if such a reaction were to occur, it might manifest with fever, chills, rigors, headache, rash, urticaria, angioedema, pruritis, arthralgias, hypo- or hypertension, bronchospasm, or other symptoms.

Treatment recommendations are provided below and may be modified based on local treatment standards and guidelines as medically appropriate:

Remain at bedside and monitor subject until recovery from symptoms.

• **For Grade 1 symptoms:** (Mild reaction; infusion interruption not indicated; intervention not indicated)

Infusion rate may be slowed or interrupted and restart the infusion at 50% of the original infusion rate when symptoms resolve; if no further complications ensue after 30 minutes, the rate may be increased to 100% of the original infusion rate. Monitor subject closely.

The following prophylactic premedications are recommended for future infusions: diphenhydramine 50 mg (or equivalent) and/or paracetamol 325 to 1000 mg (acetaminophen) at least 30 minutes before additional nivolumab administrations, slowing infusion rate as above.

• **For Grade 2 symptoms:** Moderate reaction requires therapy or infusion interruption but responds promptly to symptomatic treatment (e.g., antihistamines, non-steroidal anti-inflammatory drugs, narcotics, corticosteroids, bronchodilators, IV fluids); close observation for recurrence and treatment medications may need to be continued for 24-48 hours, and no further nivolumab will be administered at that visit.

Stop the nivolumab infusion, begin an IV infusion of normal saline, and treat the subject with diphenhydramine 50 mg IV (or equivalent) and/or paracetamol 325 to 1000 mg (acetaminophen); remain at bedside and monitor subject until resolution of symptoms. Corticosteroid or bronchodilator therapy may also be administered as appropriate. If the infusion is interrupted, then restart the infusion at 50% of the original infusion rate when symptoms resolve; if no further complications ensue after 30 minutes, the rate may be increased to 100% of the original infusion rate. Monitor subject closely. If symptoms recur, re-administer diphenhydramine 50 mg IV, and remain at bedside and monitor the subject until resolution of symptoms. The amount of study drug infused must be recorded on the electronic case report form (eCRF). The following prophylactic premedications are recommended for future infusions: diphenhydramine 50 mg (or equivalent) and (acetaminophen) (or paracetamol) 325 to 1000 mg should be administered at least 30 minutes before additional nivolumab administrations. If necessary, corticosteroids (recommended dose: up to 25 mg of IV hydrocortisone or equivalent) may be used.

• **For Grade 3 or Grade 4 symptoms:** (Severe reactions)

- Grade 3 symptoms: prolonged (i.e., not rapidly responsive to symptomatic medication and/or brief interruption of infusion); recurrence of symptoms following initial improvement; hospitalization indicated for other clinical sequelae (e.g., renal impairment, pulmonary infiltrates).
- Grade 4 symptoms: (life threatening; pressor or ventilatory support indicated): Nivolumab will be permanently discontinued.

Immediately discontinue infusion of nivolumab. Begin an IV infusion of normal saline, and bronchodilators, epinephrine 0.2 to 1 mg of a 1:1,000 solution for subcutaneous administration or 0.1 to 0.25 mg of a 1:10,000 solution injected slowly for IV administration, and/or diphenhydramine 50 mg IV with methylprednisolone 100 mg IV (or equivalent), as needed. Subject should be monitored until the investigator is comfortable that the symptoms will not recur.

Investigators should follow their institutional guidelines for the treatment of anaphylaxis. Remain at bedside and monitor subject until recovery from symptoms.

In the case of late-occurring hypersensitivity symptoms (e.g., appearance of a localized or generalized pruritis within 1 week after treatment), symptomatic treatment may be given (e.g., oral antihistamine, or corticosteroids). Additional treatment prior to next dose as per guidelines above.

Please note that late occurring events including isolated fever and fatigue may represent the presentation of systemic inflammation. Please evaluate accordingly.

